### **7.1.2. Aim 2:**

Analyses here will assess changes in craving and depression symptom scores as mediators of bupropion treatment effects at weeks 10 of treatment and 24 weeks post-TQD. These measures are continuous difference scores. Our sample of 360 is well above the minimum sample of 200 recommended for such analyses (169-170). The mediation hypotheses will examine the proportion of variance in treatment effect explained (171-172), and we will test each mediation hypothesis with a z-score generated using the delta method. Our sample of 360 gives us 80% power to observe small effects in a 1-sample test ( $\delta = 0.16$ ) when testing at  $\alpha = 0.05$ . There are 2 proposed mediating pathways (depression and craving) between treatment and outcome, so our type-1 error will be corrected to 0.025. A sample of 360 gives us 80% power to detect small-to-medium effects ( $\delta=0.35$  SD) for changes in the proposed mediators, which we have seen in previous trials (15, 52).

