### **7.2.3. Specific Aim 2: Assess changes in depression symptoms and craving as mediators of bupropion's effect on quit rates.**

We will use a regression-based path model approach to examine mediation of treatment effects based on MacKinnon et al. (175). All variables will be standardized for the analyses. The two suspected mediators will be entered as standardized pre-post differences, continuously distributed and treated as normal in linear regression. The effects of treatment arm on

CONFIDENTIAL

mediators, and of mediators on outcome, will be assessed using linear regression and standardized variables. We will focus on changes in mediators from baseline to week 3, since abstinence-induced withdrawal effects typically peak within the first 3 weeks of cessation (174), but we can examine delayed changes to weeks 5, 7, and 10 as well. Assuming that treatment predicts our mediators, we will then assemble the path model using standard structural equation modeling approaches. The path model partitions the effect of treatment on outcome into direct (and unexplained) effects vs. mediated effects. We will then test the overall mediation hypothesis using the proportion of treatment effect explained (171-172), and the strength of each mediating pathway. To do this, we will estimate the model for standardized treatment predicting abstinence without mediators to estimate the direct effect of treatment in the unadjusted model ( $\hat{\beta}^{\dagger}$ ). We will then test whether treatment predicts each of the suspected mediators and, in turn, test whether mediators predict abstinence in an adjusted treatment model and estimate the effect of treatment in the mediator adjusted model  $\hat{\beta}^*$ . Finally, we will calculate the proportion of treatment effect explained, which is calculated as  $(\hat{\beta}^{\dagger} / \hat{\beta}^*)$ ; the standard error for this quantity is calculated using the delta method, and the mediation hypothesis will be tested using a z-test. Individual pathways will be tested using products of the coefficients along each path using a delta-method based z-test.

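### Aim 2 defines the proportion of treatment effect explained as an inverted ratio that cannot be a proportion, and gives its z-test no null value

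*Combined protocol and SAP*

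**What the plan says.** Section 7.2.3 sets out the mediation analysis for Specific Aim 2, with change in depression score and change in craving as the two mediators. The overall test is described as follows: "We will then test the overall mediation hypothesis using the proportion of treatment effect explained (171-172), and the strength of each mediating pathway".

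Two coefficients are defined in turn. A model without mediators is fitted "to estimate the direct effect of treatment in the unadjusted model", giving β†. A second model includes the mediators, "and estimate the effect of treatment in the mediator adjusted model", giving β*. The section continues: "Finally, we will calculate the proportion of treatment effect explained, which is calculated as" β†/β*. On inference it says that "the standard error for this quantity is calculated using the delta method, and the mediation hypothesis will be tested using a z-test". No null value is given. The pathways have their own test: "Individual pathways will be tested using products of the coefficients along each path", again with a delta-method z.

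The power text in section 7.1.2 says "and we will test each mediation hypothesis with a z-score generated using the delta method" and "Our sample of 360 gives us 80% power to observe small effects in a 1-sample test", with δ = 0.16. It then lowers alpha to 0.025 because there are two pathways. It gives no null for the ratio either.

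**The concern.** The numerator and denominator are the wrong way round, and nothing is subtracted from 1. An unadjusted effect divided by an adjusted effect exceeds 1 whenever part of the effect is mediated, so it cannot be read as a share.

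The missing null makes this worse. A delta-method z described as a one-sample test suggests estimate over standard error, that is, a null of 0. The printed ratio equals 1 when there is no mediation, so a test against 0 would declare mediation precisely when there is none. When mediation is complete the denominator is zero and the estimate is unstable.

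At stake are the percentage reported for a named specific aim and the overall mediation test. That test could contradict the pathway tests reported beside it. The comparisons in H1 to H3 do not use this quantity.

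**Working it through.** **The plan's own figure.** Section 7.1.2 claims 80% power for δ = 0.16 and N = 360. Power = Φ(δ√N − z), with 0.16 × √360 = 3.036.
- Two-sided alpha 0.05: Φ(3.036 − 1.960) = 85.9%.
- Two-sided alpha 0.025: Φ(3.036 − 2.241) = 78.7%.

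The figure is therefore reproduced, within 2 points, only at the corrected alpha of 0.025, although its sentence names 0.05. It does not reveal the null for the ratio.

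**Algebra.** Let p = 1 − β*/β† be the mediated share. Then β* = (1 − p)β† and β†/β* = 1/(1 − p).

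| Mediated share p | Printed β†/β* | 1 − β*/β† |
|---|---|---|
| 0 | 1.00 | 0 |
| 0.25 | 1.33 | 0.25 |
| 0.50 | 2.00 | 0.50 |
| 0.75 | 4.00 | 0.75 |
| 0.90 | 10.0 | 0.90 |
| 1 | undefined | 1 |

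A leading 1 − lost in typing would not repair this: 1 − β†/β* = −p/(1 − p), which is −1 at p = 0.5. Inverting alone, β*/β†, gives the unexplained share 1 − p. Both changes are needed.

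**Simulation inputs.** N = 360, 180 per arm (section 5.3). Quit rates are 21.2% and 35.9% (section 7.1.1), with mean 0.2855 and difference 0.147, so the standardised total effect is 0.147 × 0.5 / √(0.2855 × 0.7145) = 0.163. There are two mediators, each shifted 0.35 SD (section 7.1.2). The models are linear on standardised variables (section 7.2.3). The delta-method standard error uses the joint covariance of β† and β*, with 4,000 replicates per scenario. The mediator-to-abstinence path strengths are assumed.

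Rejection rates at two-sided alpha 0.05, with 0.025 in brackets:

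| Scenario | Printed ratio | Ratio against 0 | Ratio against 1 | 1 − β*/β† against 0 |
|---|---|---|---|---|
| None: mediators move but do not drive abstinence | median 1.00 | 98.7% (98.4%) | 1.3% (0.3%) | 0.5% (0.1%) |
| Half mediated | median 1.89 | 65% (60%) | 17% (6%) | 87% (76%) |
| Fully mediated | interquartile range −4.7 to 6.8 | 5.6% (4.0%) | 3.3% (0.9%) | 94% (91%) |

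**Sensitivity.**
- *Other path sizes.* One mediator with a standardised treatment path of 0.3, binary abstinence, alpha 0.025. With no mediation, ratio against 0 rejects 99.3% to 99.9% and against 1 rejects 0.0% to 0.1%. Half mediated: 58% and 2.6%, corrected form 69%. Fully mediated: 5.6% and 1.5%, corrected form 73%.
- *Main set-up with a binary outcome, alpha 0.05.* Ratio against 0 rejects 98.7% with no mediation and 8.6% with complete mediation; the corrected form gives 0.4% and 76%. In the complete case the total effect falls to 0.129 because probabilities are clipped at 0.
- *Standard error ignoring the covariance.* The plan does not say which is used. With no mediation, rejection against 0 at alpha 0.05 falls to about 61%.
- *No treatment effect and no mediation.* The ratio still rejects 0 in 48% to 74% at alpha 0.05, so it does not serve as a test of the treatment effect either.

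**Conflict with the pathway tests** (pathways at 0.025, ratio at 0.05 against 0). With no mediation, the ratio is significant while neither pathway is in 98% of trials. With complete mediation, a pathway is significant while the ratio is not in 93%.

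**The case against.** **The null of 0 is inferred.** The one-sample sentence in section 7.1.2 may describe the pathway tests rather than the ratio. Against 1, the ratio's own no-mediation value, there are almost no false positives. This stands as a limit on the false-positive figures. It does not rescue the quantity: the reported percentage is wrong under either null, and against 1 the test detects half mediation in 17% of trials and complete mediation in 3.3%.

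**Earlier steps would expose a false signal.** The plan builds the path model on the assumption that treatment predicts the mediators, and it tests whether mediators predict abstinence before computing the ratio. In the main no-mediation case, that second test is non-significant for both mediators in about 95% of runs (0.025 each). This is fair, but the ratio is not made conditional on it, so the report would carry two contradictory results.

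**The full-mediation case is strong.** It needs mediator-to-abstinence paths of about 0.47 each. The model then explains about 46% of the variance in abstinence, or about 64% if the mediators correlate 0.4 within arm. This also stands. At a milder 25% mediated, alpha 0.05, the ratio rejects 0 in 91% and 1 in 8%, against 51% for the corrected form. Rejection against 0 still falls as mediation rises.

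**An analyst would notice.** A proportion above 1 is conspicuous, and p can be recovered as 1 − 1/ratio. That is likely true, but the formula and null should be settled before unblinded data are seen.

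**Conclusion.** The concern holds. As written, the proportion of treatment effect explained equals 1/(1 − p), which is never a proportion for 0 < p < 1, and its z-test has no stated null. This follows from the plan's own definitions on any scale; it assumes only that the mediated share is defined by the difference between the two coefficients.

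The size of the damage to the test depends on the null and on assumed path strengths. Against 0, the test signals mediation most often when there is none. Against 1, it is safe but has little power. The error is confined to the proportion-explained part of Aim 2. It should be corrected before analysis, but it does not threaten the primary efficacy result.

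**What to change.** In section 7.2.3:

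- Define the proportion explained as 1 − (β*/β†), and call β† the total effect, since a model without mediators cannot isolate a direct one.
- State the null as 0 and the alpha for this overall test.
- Compute the standard error from the joint covariance of the two estimates, or by bootstrap.
- Fit both models on the same scale and the same participants. The plan already standardises all variables. The participant set needs stating because missing abstinence counts as smoking, whereas section 7.2.1 gives no matching rule for a wholly missing mediator score.
- Keep the product-of-coefficients pathway tests at 0.025. A sentence on how the overall and pathway results combine would be useful but is not essential to the correction.

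The cost is one formula and a few sentences before analysis. Data collection and sample size do not change.

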### 5.3. Method for Assigning Participants to Treatment Groups

Participants will be randomly assigned to one of two treatment conditions: Bupropion 300 mg/day (n = 180) or placebo (n = 180). We will use small-block randomization by site (Penn or MATER) provided by [name], the study biostatistician. A PHQ-9 score of 10 or greater will be used to identify major depression and stratify the randomization on it. Study site (Penn or MATER) will be the second of the two stratification variables. Study staff and the Investigational Drug Service (IDS) staff will be responsible for medication randomization. The process for randomization is: 1) The research coordinator will complete a “randomization form,” which includes the variables to be entered into the randomization program and fax or email the form without protected health information to the UPenn site; 2) A designated study staff member

Table 1: Medication Dispensing Schedule

	Medication Dispensed For	Morning Dose	Evening Dose	Total Daily Dose
Visit A: Screening	N/A	No medication	No medication	
Visit B: Baseline	Wk 1	150 mg	No medication (for first 3 days); then 150 mg	150 mg
Visit C: Wk 1	Wk 2 through Wk 5	150 mg	150 mg	300 mg
Visit D: Wk 3	N/A	N/A	N/A	N/A
Visit E: Wk 5	Wk 6 through Wk 10	150 mg	150 mg	300 mg
Visit F: Wk 7		150 mg	150 mg	300 mg
Visit G: Wk 10	Endpoint	No medication	No medication	N/A

CONFIDENTIAL

This material is the property of the University of Pennsylvania. Do not disclose or use except as authorized in writing by the study sponsor

Visit H: Wk 24 Post-TQD	N/A	No medication	No medication	N/A
Visit I: 2 wk postpartum	N/A	No medication	No medication	N/A
Visit J: 6 wk postpartum	N/A	No medication	No medication	N/A

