## 7. Statistical Plan

### 7.1. Power

A power analysis is provided only for the primary aims because the exploratory aim is hypothesis generating. Most of our power calculations were approximated as 2-sided t- or z-tests, with  $\alpha = 0.05$ , using PASS Software (Power and Sample Size, NCSS Software, Kaysville, UT). Equivalence testing was approximated as two one-sided tests, with  $\alpha = 0.025$  each.

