#### 7.1.1. Aim 1:

The primary efficacy analysis (**H1**) is a comparison in week 10 (of treatment) and week 24 post-TQD of CO-confirmed 7-day point prevalence quit rates for the placebo and bupropion groups. For the week-10 comparison, we expect that the quit rates in the placebo and bupropion arms would approximate those reported in bupropion trials in the general population of smokers (i.e., placebo = 21.2%; bupropion = 35.9%, OR = 2.1; ref. 44). A sample of 360 provides 88% power to detect a significant between-group effect. The OR for bupropion treatment is similar at 24 weeks, based on Jorenby et al. (168) and our own data, and results from 10 and 24 weeks are highly correlated ( $\rho > 0.7$ ). Thus, we have 80% power to detect a significant difference between treatment arms.

Safety analyses (**H2**) will examine maternal safety across the 10-week treatment and 24-week follow-up periods and fetal and birth outcomes. Key maternal and fetal outcomes to be compared across treatment groups include rates of moderate-to-severe side AEs of bupropion (from the AE checklist). Key birth outcomes will include Apgar scores, birth weight, duration of pregnancy, rate of obstetrical complications, and need for NICU admission. These analyses will involve a test of equivalence because we cannot use standard statistical tests to conclude that a non-significant comparison shows that the drug is safe (i.e., "the absence of evidence is not evidence of its absence"). In our past study with bupropion, 45% of bupropion-treated participants reported no moderate-to-severe AEs, vs. 47% of participants on placebo, a 2% difference. With the present sample size, we will have 82% power to detect similar equivalence between treatment arms on the frequency of moderate-to-severe AEs over the course of the trial, given that AEs are not significantly different between treatment arms, using an equivalence window of 0.30 to 0.60. Likewise, Oncken et al. (47) reported 38% AEs for the placebo group

CONFIDENTIAL

and 25% in the nicotine group. An equivalence test with placebo and bupropion groups both at 30% and an equivalence window for bupropion of +/-15% provides 81% power.

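### Section 7.2.3 tests each mediation pathway with a delta-method z-test on the product of coefficients. The test is conservative, and the power it costs depends on a mediator-to-abstinence effect that the plan does not give.

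*Combined protocol and SAP*

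**What the plan says.** Section 7.2.3 plans linear regressions on standardized variables for the effect of treatment on each mediator (path a) and of each mediator on abstinence given treatment (path b). It then tests the two pathways separately: "Individual pathways will be tested using products of the coefficients along each path using a delta-method based z-test". Ahead of this it sets an overall mediation test based on the proportion of the treatment effect explained, with its own delta-method standard error.

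Section 7.1.2 sets the error rate: "There are 2 proposed mediating pathways (depression and craving) between treatment and outcome, so our type-1 error will be corrected to 0.025". It gives two power statements. The first is "Our sample of 360 gives us 80% power to observe small effects in a 1-sample test", with an effect of 0.16 at alpha 0.05. The second is "A sample of 360 gives us 80% power to detect small-to-medium effects", set at 0.35 SD for changes in the mediators. Neither section gives an effect for the mediator-to-abstinence path or a power for the product test. Section 7 names no bootstrap, product-distribution interval or joint-significance rule.

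**The concern.** The product of two normal estimates is not itself normal. It is close to normal only when at least one factor is large relative to its standard error. Otherwise it is peaked at zero and, when both effects are real, skewed. A symmetric z-test then rejects too rarely under the null and misses pathways whose two component paths are both clear.

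Aim 2 is a specific aim with its own power section. A negative pathway result could reflect the test and not the data, and the plan's power statements would not reveal this.

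**Working it through.** **Inputs.** From the documents:
- 180 per arm (section 5.3).
- Path a of 0.35 SD and alpha 0.025 per pathway (section 7.1.2).
- Two-sided testing, from section 7.1: "Most of our power calculations were approximated as 2-sided t- or z-tests, with" alpha 0.05.
- For the simulated trials only, the placebo quit rate of 21.2% (section 7.1.1).

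Assumed: the strength of path b, expressed as its expected z, because the documents give none.

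**The plan's own figures.** The standard error of path a is √(2/180) = 0.1054 SD, so the expected z_a is 0.35/0.1054 = 3.32. The critical value at two-sided 0.025 is 2.241.
- Power for 0.35 SD is Φ(3.320 − 2.241) = 86.0%, against a stated 80%. The effect detectable with 80% power is (2.241 + 0.842) × 0.1054 = 0.325 SD.
- For the one-sample effect, 0.16 × √360 = 3.036 and Φ(3.036 − 1.960) = 85.9%, against a stated 80%.

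Neither figure reproduces at its stated alpha; both understate power. Neither is a power for a product of two paths. Only the 0.35 SD effect is carried forward.

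**The statistic.** With z_a = a/se_a and z_b = b/se_b, the first-order delta-method (Sobel) z is

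ab / √(a²·se_b² + b²·se_a²) = z_a·z_b / √(z_a² + z_b²).

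This is always smaller in size than either z_a or z_b. If the two are equal, each must exceed 2.241 × √2 = 3.17 to reach significance. With z_a = 2.5 and z_b = 5.0 the result is 12.5/√31.25 = 2.236, below 2.241, although each path is clearly significant alone.

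**Size at nominal 2.5%, one path null** (4 million draws of independent z_a and z_b):

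| Expected z of the non-null path | Delta-method z-test | Joint significance |
|---|---|---|
| 2.8 | 0.21% | 1.78% |
| 3.32 (plan's path a, b = 0) | 0.38% | 2.16% |
| 4 | 0.68% | 2.41% |
| 4.7 | 1.0% | not run |
| 5 | 1.1% | 2.5% |
| 6 | 1.5% | 2.5% |
| 8 | 1.9% | 2.5% |
| 20 | 2.4% | 2.5% |

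With both paths null, the delta-method size is below 0.01% and joint significance has 0.025² = 0.06%.

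**Power at the plan's path a (z_a = 3.32):**

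| Assumed expected z of path b | Delta-method z-test | Joint significance | Loss, points |
|---|---|---|---|
| 1.5 | 6.5% | 19.7% | 13 |
| 2.0 | 14% | 35% | 21 |
| 2.8 | 34% | 61% | 28 |
| 3.32 | 48% | 74% | 26 |
| 4.0 | 64% | 83% | 19 |
| 4.3 | 69% | 84% | 15 |
| 5 | 76% | 86% | 9 |
| 6 | 81% | 86% | 5 |
| 10 | 85% | 86% | 1 |

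Both tests are capped at 86.0%, the power of path a alone.

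**Check on simulated trials.** For each setting, 6,000 trials were run with N = 360, two mediators, a binary outcome (intercept at the 21.2% placebo rate, assumed direct effect 0.4 on the log-odds scale) and least-squares paths.
- With a = 0.35 SD and b = 0, size was 0.27% for the delta method, 2.20% for joint significance and 2.03% for the Monte Carlo product interval.
- With an assumed mediator log-odds effect of 0.4 per SD, power was 46.5%, 72.2% and 72.8%. At 0.5 it was 66.4%, 84.1% and 84.8%.
- The Monte Carlo interval stayed within about 1 point of joint significance. Its highest simulated size was 2.9%, with a simulation error of about √(0.025 × 0.975/6,000) = 0.2 points.

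The percentile bootstrap was not part of this power comparison.

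**The case against.** - **The error is on the safe side.** False positives are not inflated, and Aim 1 and the safety analyses are untouched. This stands, and it limits the point to an efficiency loss in a mechanistic aim.
- **The component tests are planned anyway.** Section 7.2.3 tests whether treatment predicts each mediator and whether each mediator predicts abstinence with treatment in the model. Both p-values will therefore exist, and a real pathway need not go unseen. This stands in part, but the plan does not make the pair its decision rule; the product z-test decides.
- **The requirement that treatment first predict the mediator might seem to change the picture.** It does not. The delta-method z is always below z_a, so at the same alpha a rejection already implies a significant path a.
- **The loss depends on a path the documents do not describe.** This stands fully. From "A sample of 360 gives us 80% power to detect small-to-medium effects" a reader might infer that the plan expects a modest mediator-to-abstinence path. That sentence concerns changes in the mediators, which is path a only. A strong path b would make the loss small.
- **The alternatives are not exact.** They too are very conservative when both paths are null.

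**Conclusion.** The point holds in conditional form. The pathway test in 7.2.3 is conservative. At the plan's own 0.35 SD its size is about 0.4% when path b is null, against a nominal 2.5%. For path b at an expected z of 3.3 to 4.3, it gives up about 26 to 15 points of power against joint significance or a product-distribution interval. With path a held at 0.35 SD, the loss over wider assumptions runs from about 1 to 28 points. The tabulated figures rest on independent, normal path estimates and on an assumed path b.

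Three stronger readings are tempting but unsupported:
- That the error rate is always under 1%. It passes 1% once the non-null path exceeds an expected z of about 4.7. A mediator that strongly predicts abstinence but is not moved by treatment is a natural null here, and in that case the defect shrinks.
- That 15 to 26 points is a fixed property of the test. It belongs to one range of an effect the documents omit.
- That section 7.1.2 plans the same product test when it says "we will test each mediation hypothesis with a z-score generated using the delta method". That clause follows the statement about the proportion explained, and 7.1.2 does not mention products.

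**What to change.** In section 7.2.3 only, replace the delta-method z-test of each product with a two-sided 97.5% confidence interval for that product. Either a Monte Carlo (distribution-of-product) interval or a percentile bootstrap, for example 5,000 resamples within arm, would serve. Declare a pathway supported when its interval excludes zero. Name one method in advance, with the number of draws and the seed.

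The interval uses the same regressions, data and sample size, and can be run in the software the plan already names (Stata, SAS or R). The cost is a change of wording, a few lines of code and a little computing time. The remaining downside is that these methods are also conservative when both paths are null.

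This change does not address the proportion-explained test of the overall mediation hypothesis or the z-score attached to it in 7.1.2. Those are a separate matter.
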